4.1 Overview of Treatment Plan

This is a randomized open-label clinical trial designed to assess the efficacy of caspofungin for preventing IFI (including IA) compared to antifungal prophylaxis with an azole (fluconazole or voriconazole), the standard therapies used in most COG institutions as prophylaxis in patients undergoing HCT.

At the time of enrollment, the enrolling center will declare whether the comparator arm will be fluconazole or voriconazole based upon that institution's standard of care and the choice of comparator should remain constant for the duration of the study.

Patients who consent to participate in ACCL1131 will be randomly assigned to antifungal prophylaxis with either an azole or caspofungin. Treatment with any antifungal prophylaxis initiated prior to enrollment must be terminated prior to starting protocol-directed antifungal therapy. Protocol prophylaxis will be started within 24 hours of transplant (Day 0). Administration of antifungal prophylaxis will continue until (a) HCT Day +42; OR (b) Day of Hospital Discharge; OR (c) Patient meets any off-protocol criteria (Section 8.1). Following discontinuation of study medications, institutions may revert to local standard of care for post-graftment antifungal prophylaxis.

If other systemic antifungal therapy is initiated for empiric therapy or treatment of suspected infection, then protocol prophylaxis should be held and assigned prophylaxis should resume when other systemic antifungal therapy is discontinued if this occurs prior to Day +42, Day of Hospital Discharge, or at the time a patient is taken off-protocol therapy (see Section 8.1).

Fluconazole and voriconazole may be administered either intravenously (IV) or orally. Caspofungin is only available as an IV formulation.

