7.1 Required and Optional Clinical, Laboratory and Disease Evaluations

All baseline studies must be performed prior to starting protocol therapy unless otherwise indicated below. These studies should be obtained even if the patient has been removed from protocol therapy, unless they are off study (see Section 8.0).

| STUDIES TO BE OBTAINED | Baseline | Day 0 to Day 42 (or Discharge) | Day 100^ End of ACCL1131 Monitoring |
|---------------------------------------|----------|-----------------------------------|---|
| REQUIRED | | | |
| CBC, differential, platelets | X | Twice Weekly | X |
| Performance Status | X | | X |
| Creatinine, AST, ALT, bilirubin | X | Twice Weekly | X |
| Albumin | X | Weekly | X |
| IFI checklist | | X* | X* |
| GVHD Scoring | | Weekly(after Day 14) | X |
| OPTIONAL (IF PATIENT CONSENTS) | | | |
| Beta-D Glucan Assays | | Weekly@ | |
| Sample for SNP Genotyping | X# | | X# |

^Day 100-114

*Submit relevant IFI checklist documents via the Document Imaging System: [contact] as of Day 42 and Day 100. See Section 10.2 for further details.

@ See Section 13 for details. It is suggested that specimens be obtained on Thursdays but other days are acceptable if more convenient. During the prophylaxis period, documentation of exposure or lack of exposure to each of the following will be performed: amoxicillin-clavulanate and intravenous immunoglobulin.

See Section 14 for details. End of study sample may be collected on Day +100 +/-7 days.

This table only includes evaluations necessary to answer the primary and secondary aims. Obtain other studies as indicated for good clinical care.

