13.4 Patient Accrual

All patients to be enrolled on ACCL1131 will be offered the chance to participate in this ancillary fungal infection screening study. Those who consent will undergo weekly Fungitell Assay testing from the time of the HCT until Day +42 or until withdrawal from the study for any reason. It is suggested that specimens be obtained on Thursdays but other days are acceptable if more convenient. For those patients discharged prior to Day +42 weekly outpatient testing will be performed when possible. Each patient will have the potential for 7 separate testing points (once a week for 7 weeks). The proposed ancillary study will concurrently enroll patients from the parent trial with a goal of enrolling 400 patients.

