13.8 Factors Resulting in False Positive Results

A number of medications, medical interventions, and infections have been suggested as possible causes of false positive results for BG testing.⁶⁸⁻⁷⁰ Table 2 lists the potential causes of false positive results reported in the literature. It is anticipated that recipients of a HCT will have reason to be exposed to a number of these medications, infusions and/or medical interventions. Additionally, *Pneumocystis jiroveci* infection is also considered a cause of a “false positive” BG test. Technically this is not a true false positive as the Fungitell Assay is detecting BG from the cell wall of *Pneumocystis jiroveci* as it would for other fungal infections. However, in this instance it is considered a “false positive” as the treatment of choice for this infection is trimethoprim-sulfamethoxazole as opposed to a typical anti-fungal agent. A sensitivity analysis (as described in Section 13.9.4 below) will be performed to investigate the impact of these false positive inducing factors on the operating characteristics of the 2 biomarkers. The starred factors are likely to be the most clinically relevant and thus they will be focused on.

| Table 2. Potential factors resulting in false positive testing for (1→3) beta-D glucan | |
|---|--|
| Medications | *Amoxicillin-clavulanate |
| Infusions | *Intravenous immune globulin Cellulose filters for IV infusion Albumin |
| Medical interventions | Hemodialysis with cellulose filter Gauze packing on serosal Surfaces |
| Other infections | * Pneumocystis jiroveci |

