Additionally, the ROC curves will be used in an exploratory analysis to identify the threshold for the biomarker assay that optimizes the diagnostic test's sensitivity while maintaining a reasonable specificity. The identified thresholds will be used to categorize each patient as "likely to have IFI" and "not likely to have IFI". Once these 2 sub-groups are defined we will calculate the incidence rates of IFI for each sub-group and compare them. Because the anticipated incidence for IFI may be variable between the two study

arms (those receiving an azole and those receiving caspofungin) this approach will have to be done at the level of each study arm. The incidence rates will be compared statistically using Pearson's Chi-square analysis.

Finally, to further explore the ideal utility and interpretation of each biomarker, serial testing results will be explored. For this analysis the Fungitell beta-D-glucan Assay will be considered positive when a patient has 2 consecutive test results ≥ 80 pg/mL. Operating characteristics and ROC curves will be constructed in a similar manner as discussed above.

13.9.4 Sensitivity Analysis:

Sensitivity analyses will be explored for the reasons expressed in Section 13.7.1 and 13.8. The first sensitivity analysis will attempt to identify the direction and magnitude of the bias resulting from the availability of clinical BG testing performed outside of the ancillary study. Such testing has the potential to change the treating clinician's approach for diagnosing an IFI. It is possible that these test results could result in more or less investigation (e.g. radiologic imaging) to identify an IFI, which could ultimately impact on the incidence of identified IFI. Therefore, in addition to calculating the operating characteristics for all patients enrolled, the same operating characteristics will be calculated after excluding all patients that had at least 1 biomarker test result available to the treating clinician.

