The second sensitivity analysis will be performed to explore the impact of the various factors described in Section 13.8 that may contribute to a positive result for the biomarker. False positive results would impact the final interpretation of sensitivity and PPV for each of the assays. However, it is also possible that one of the factors listed in Table 2 is present in a patient that truly has an IFI. Therefore, we plan to still include all patients in the primary analysis for calculation of the assay's operating characteristics. In this sensitivity analysis, we will eliminate all patients with a positive test that correlates in time with at least 1 of the starred factors listed in Table 2.

13.10 **Significance**

Fungal infections continue to be major contributors to morbidity and mortality in children undergoing HCT. Although antifungal prophylaxis in these patients will reduce the frequency of IFI, it will not eliminate the risk of these devastating infections. Early diagnosis and therapeutic modifications are paramount to improving patient outcomes. The Fungitell beta-D-glucan Assay is a potential diagnostic tool that could improve the time to diagnosis of IFI. More definitive data regarding the operating characteristics of these 2 biomarkers interpreted separately and simultaneously in the setting of a large pediatric cohort receiving anti-fungal prophylaxis are necessary. Evaluating the biomarker first as an integrated test will provide valuable information regarding the utility of each test for future pediatric patients being treated under similar circumstances. It is important to realize that the results of this study (either to support or not support the routine clinical use of the biomarker) will have an important impact on the provision of future clinical care. If the results support the biomarker as an adjunctive diagnostic tool for identifying IFI, then clinicians will be better informed on the clinical application of the assay results. However, if the assay does not perform well in identifying IFI, then clinicians will know that this assay is not useful in this clinical scenario and thus will not order the test. This would result in the conservation of finite resources and redirect the focus of researchers to other modalities for diagnosing fungal infections.

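### The false-positive sensitivity analysis of the beta-D-glucan assay deletes exposed patients only when they test positive, so under the single-test definition the direction of change is fixed in advance and the plan gives no benchmark for its size.

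*Combined protocol and SAP*

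**What the plan says.** Section 13.8 lists factors reported to cause positive beta-D-glucan results without the target infection and stars three for attention: amoxicillin-clavulanate, intravenous immune globulin and *Pneumocystis jiroveci*. Section 13.9.4 then plans two sensitivity analyses.

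- The first deals with local beta-D-glucan testing. It recalculates the operating characteristics "after excluding all patients that had at least 1 biomarker test result available to the treating clinician".
- The second deals with the starred factors: "we will eliminate all patients with a positive test that correlates in time with at least 1 of the starred factors" in Table 2. Its stated reason is that "False positive results would impact the final interpretation of sensitivity and PPV for each of the assays". Because a factor may also be present in a patient who truly has an invasive fungal infection (IFI), "we plan to still include all patients in the primary analysis".

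Section 13.9.2 scores each patient by a single positive test against proven or probable IFI. On exposure data, Section 7.1 says: "During the prophylaxis period, documentation of exposure or lack of exposure to each of the following will be performed: amoxicillin-clavulanate and intravenous immunoglobulin".

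**The concern.** The two sensitivity analyses exclude on different grounds. The first excludes on whether a local result was available, whatever the study assay showed. The second excludes on the study assay result itself, combined with exposure. Exposed patients who tested positive leave the true-positive and false-positive cells, while exposed patients who tested negative stay in the false-negative and true-negative cells. The table is trimmed on one side only.

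A reader would turn to this analysis to learn whether immune globulin or amoxicillin-clavulanate degrades the assay. A rise in specificity would look like evidence of factor-caused false positives, and a fall in sensitivity like evidence that some apparent detections were due to the factor. The deletion rule produces both by itself. Sensitivity is the parameter that Section 13.9.2 ranks highest, and Section 13.2 sets a hypothesis of more than 90% for it, so an artificial fall below 90% would be easy to misread.

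**Working it through.** **Inputs.** The planned cohort is 400 patients, 200 per arm, with IFI rates of 7% and 2% (Section 13.9.1). Sensitivity 0.90 is taken from the hypothesis in Section 13.2. Specificity 0.85 comes from the meta-analysis in Section 13.1.3, and the 15% of healthy children at or above 80 pg/mL in Section 13.7.1 points to the same value. The documents do not give the share of positives that coincide with exposure, so it is assumed and varied.

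**The plan's own figure.** 200 × 0.07 + 200 × 0.02 = 14 + 4 = 18 IFIs, as stated. That leaves 382 patients without IFI. The plan gives no figure for this sensitivity analysis.

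**Base table.** TP = 18 × 0.90 = 16.2 and FN = 1.8. TN = 382 × 0.85 = 324.7 and FP = 57.3.

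**Direction.** Suppose the rule removes b true positives and a false positives.

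- Sensitivity becomes (TP − b)/(TP − b + FN), which is never above TP/(TP + FN).
- Specificity becomes TN/(TN + FP − a), which is never below TN/(TN + FP).
- NPV = TN/(TN + FN) cannot move, because no negative is removed.

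A full enumeration with 18 IFI and 382 non-IFI patients covered 73,724 removal patterns and found no exception.

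**A factor with no effect.** Let e be the share of positives that are exposed, the same among true and false positives. Then Se′ = Se(1 − e)/[Se(1 − e) + 1 − Se] and Sp′ = Sp/[Sp + (1 − Sp)(1 − e)].

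| e | Sensitivity | Specificity |
|---|---|---|
| 0 | 0.900 | 0.850 |
| 0.10 | 0.81/0.91 = 0.890 | 0.85/0.985 = 0.863 |
| 0.25 | 0.675/0.775 = 0.871 | 0.85/0.9625 = 0.883 |
| 0.50 | 0.45/0.55 = 0.818 | 0.85/0.925 = 0.919 |

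PPV stays at 16.2/73.5 = 0.220 throughout, because both of its cells shrink by the same factor.

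**Does the size carry information?** Assume 40% of non-IFI patients are exposed and specificity in the unexposed is 0.85. Unexposed false positives are then 0.6 × 0.15 = 0.09 of the group. The last column is the change that the same overall specificity would show under no effect, from the Sp′ formula with e = 0.40.

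| Specificity in exposed | All patients | After deletion | Change (points) | Change expected under no effect (points) |
|---|---|---|---|---|
| 0.95 | 0.89 | 0.89/0.98 = 0.908 | +1.8 | 0.89/0.956 = 0.931, so +4.1 |
| 0.85 | 0.85 | 0.85/0.94 = 0.904 | +5.4 | 0.85/0.94 = 0.904, so +5.4 |
| 0.70 | 0.79 | 0.79/0.88 = 0.898 | +10.8 | 0.79/0.916 = 0.862, so +7.2 |

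Specificity rises in all three cases, even when exposed patients have fewer false positives. The size of the rise does follow the factor's effect, but a rise of 5.4 points means nothing until it is set beside the rise expected from the exposed share. The plan does not call for that comparison.

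**Where the direction is not guaranteed.**

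- Section 13.2 counts a positive only if it precedes the IFI diagnosis. If a later positive is scored as a miss, an IFI patient whose only positive came after diagnosis and during exposure is a false negative who is deleted. With 16 of 18 detected, removing one such patient moves sensitivity from 16/18 = 0.89 up to 16/17 = 0.94.
- Section 13.9.3 adds cut-offs of 100 and 120 pg/mL and a rule of two consecutive positives. If patients are deleted on a single result at 80 but scored on a stricter rule, some deleted patients count as negatives. Specificity can then fall and sensitivity can rise.

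**The case against.** The strongest reply has three parts.

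First, this is a descriptive robustness check. Section 13.8 takes the factors as known causes of false positives, and the analysis sets aside positives that have a competing explanation. All patients stay in the main calculation and no decision depends on the result. This stands as a limit on importance. It does not make the recalculated sensitivity and specificity interpretable, because the deletion moves them even when the factor is inert. Nor is the deletion a worst-case bound. Recoding factor-linked positives as negative would give sensitivity 0.90 × 0.75 = 0.675 and specificity 1 − 0.15 × 0.75 = 0.8875 at a 25% share, against 0.871 and 0.883 by deletion.

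Second, a reader might infer that the change in specificity carries no information at all. That goes too far. The +1.8, +5.4 and +10.8 points above separate a favourable, an inert and a harmful factor when the exposed share is the same. One can construct a real effect and a null effect that both end at 0.92, but only by giving them different exposed shares (25% and 50%). At a common 25% they end at 0.92 and 0.88. What is missing is a benchmark. PPV also keeps some information, though little with 18 expected IFIs: in that constructed pair, about 12/41 against 8/37 gives exact 95% intervals of 0.16 to 0.46 and 0.10 to 0.38.

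Third, a reader might infer that the direction is fixed under every analysis in Section 13.9. It is not, for the reasons at the end of the working. The documents do not say whether the deletion is carried over to those other definitions.

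The omission of specificity from the rationale is a wording matter, since Section 13.9.2 already reports it. It is still worth correcting. A false positive occurs in a patient without IFI and enters specificity and PPV; it bears on sensitivity only if the text means factor-caused positives in patients who do have IFI.

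**Conclusion.** The concern holds in a limited form. Under the single-positive-test definition, with the same definition used for deletion and scoring, the second sensitivity analysis can move specificity only up and sensitivity only down, or leave them unchanged. For an inert factor, with assumed sensitivity 0.90 and specificity 0.85, the shift is about 0.01 in each at a 10% exposed share of positives. At 25% the values become 0.87 and 0.88, and at 50% they become 0.82 and 0.92. The exposed shares are assumptions; the direction does not depend on them. The sign of the change is therefore uninformative, and its size needs a no-effect benchmark that the plan lacks.

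A reader might also infer that the assay's main results or the trial's efficacy conclusion are biased. The documents do not support that: the main assay calculation keeps every patient, and the trial's primary endpoint does not use this analysis. The severity is minor.

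**What to change.** Replace the deletion rule with a comparison defined by exposure, whatever the test result.

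1. For amoxicillin-clavulanate and for intravenous immune globulin, report specificity in exposed and unexposed patients with confidence intervals, and sensitivity descriptively. Use samples from the prophylaxis period, for which Section 7.1 documents exposure, and show the number of samples per patient by group, because longer stays bring both more samples and more chances of exposure.
2. If exposure dates are available, prefer a sample-level version that excludes all samples, positive or negative, inside a pre-defined exposure window. Section 7.1 does not say that dates are collected, and the case report forms are not in the documents. The planned rule itself relies on timing, yet defines no window.
3. Handle *Pneumocystis* separately. Section 13.8 says of it: "Technically this is not a true false positive as the Fungitell Assay is detecting BG from the cell wall". Section 7.1 does not list it with the two recorded exposures.
4. Name specificity in the rationale.

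**Cost.** Item 1 needs only SAP wording, but its sampling window is shorter than that of the main assay analysis. Section 4.1 says: "Administration of antifungal prophylaxis will continue until (a) HCT Day +42; OR (b) Day of Hospital Discharge". Section 13.4 carries sampling beyond discharge: "For those patients discharged prior to Day +42 weekly outpatient testing will be performed when possible". Keeping those later samples would need added exposure data. The patient-level version also loses the time link between exposure and result, which is why item 2 is preferable if dates exist.

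Strata are small. With half the cohort exposed, specificity of 162/191 in each group has an exact 95% interval of 0.79 to 0.90, which is usable. Sensitivity of 8/9 has 0.52 to 0.997, which is not. With 25% exposed and true specificities of 0.70 and 0.90, the comparison would show about 67/96 (0.60 to 0.79) against 258/286 (0.86 to 0.93), a clear separation.

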14.0 SPECIAL STUDIES SPECIMEN REQUIREMENTS FOR PATIENTS THAT CONSENT ONLY

14.1 Single Nucleotide Polymorphisms

Genotypes of interest in genes mediating immune function will be determined by review of the literature. Analysis will be performed on the Taqman Open Array Platform according to the manufacturer's instructions.

14.1.1 Sample Collection

Collect 5 mL of peripheral blood in a purple top (EDTA) tube at study entry and at end of study (Day +100 +/- 7 days), optimally when the patient has an ANC >1000/ μ L. Patients with weights less than 20 kg may have only 3 mL collected. Specimens may be shipped fresh to the BPC, where the plasma and buffy coat will be stored at -20°C.

14.1.2 Labeling:

Label the tubes with the patient's BPC #, specimen type, and date of collection.

14.1.3 Shipping:

Ship sample at room temperature by FedEx priority overnight delivery. Shipping labels can be obtained via the Biopathology Center's Kit Management application. Blood may be shipped Monday through Friday for receipt on Tuesday through Saturday. Include a COG Specimen Transmittal Form with each shipment.

The SNP sample should be shipped to:

COG Biopathology Center – ACCL1131
Nationwide Children's Hospital
[name]*
[name]
[contact]
[contact]

*Be sure to include the room number. Packages received without the room number may be returned to the sender.

15.0 BANKING SPECIMENS

If the patient consents, leftover blood samples (from the studies described in Section 14) will be returned to the BPC and banked for future research studies.

APPENDIX II: EORTC/MSG CRITERIA

Criteria for proven invasive fungal disease except for endemic mycoses³¹

| Analysis and specimen | Molds ^a | Yeasts ^a |
|--|---|---|
| Microscopic analysis: sterile material | Histopathologic, cytopathologic, or direct microscopic examination ^b of a specimen obtained by needle aspiration or biopsy in which hyphae or melanized yeast-like forms are seen accompanied by evidence of associated tissue damage | Histopathologic, cytopathologic, or direct microscopic examination ^b of a specimen obtained by needle aspiration or biopsy from a normally sterile site (other than mucous membranes) showing yeast cells—for example, Cryptococcus species indicated by encapsulated budding yeasts or Candida species showing pseudohyphae or true hyphae ^c |
| Culture | | |
| Sterile material | Recovery of a mold or “black yeast” by culture of a specimen obtained by a sterile procedure from a normally sterile and clinically or radiologically abnormal site consistent with an infectious disease process, excluding bronchoalveolar lavage fluid, a cranial sinus cavity specimen, and urine | Recovery of a yeast by culture of a sample obtained by a sterile procedure (including a freshly placed [!24 h ago] drain) from a normally sterile site showing a clinical or radiological abnormality consistent with an infectious disease process |
| Blood | Blood culture that yields a mold ^d (e.g., Fusarium species) in the context of a compatible infectious disease process | Blood culture that yields yeast (e.g., Cryptococcus or Candida species) or yeast-like fungi (e.g., Trichosporon species) |
| Serological analysis: CSF | Not applicable | Cryptococcal antigen in CSF indicates disseminated cryptococcosis |

^a If culture is available, append the identification at the genus or species level from the culture results.

^b Tissue and cells submitted for histopathologic or cytopathologic studies should be stained by Grocott-Gomori methenamine silver stain or by periodic acid Schiff stain, to facilitate inspection of fungal structures. Whenever possible, wet mounts of specimens from foci related to invasive fungal disease should be stained with a fluorescent dye (e.g., calcofluor or blankophor).

^c *Candida*, *Trichosporon*, and yeast-like *Geotrichum* species and *Blastoschizomyces capitatus* may also form pseudohyphae or true hyphae.

^d Recovery of *Aspergillus* species from blood cultures invariably represents contamination.

Criteria for probable invasive fungal disease except for endemic mycoses

Host factors^a

- Recent history of neutropenia ($< 0.5 \times 10^9$ neutrophils/L [< 500 neutrophils/mm³] for >10 days) temporally related to the onset of fungal disease
- Receipt of an allogeneic stem cell transplant
- Prolonged use of corticosteroids (excluding among patients with allergic bronchopulmonary aspergillosis) at a mean minimum dose of 0.3 mg/kg/day of prednisone equivalent for > 3 weeks
- Treatment with other recognized T cell immunosuppressants, such as cyclosporine, TNF- α blockers, specific monoclonal antibodies (such as alemtuzumab), or nucleoside analogues during the past 90 days
- Inherited severe immunodeficiency (such as chronic granulomatous disease or severe combined immunodeficiency)

Clinical criteria^b

Lower respiratory tract fungal disease^c

- The presence of 1 of the following 3 signs on CT:
 - Dense, well-circumscribed lesions(s) with or without a halo sign
 - Air-crescent sign
 - Cavity

Tracheobronchitis

- Tracheobronchial ulceration, nodule, pseudomembrane, plaque, or eschar seen on bronchoscopic analysis

Sinonasal infection

- Imaging showing sinusitis plus at least 1 of the following 3 signs:
 - Acute localized pain (including pain radiating to the eye)
 - Nasal ulcer with black eschar
 - Extension from the paranasal sinus across bony barriers, including into the orbit

CNS infection

- 1 of the following 2 signs:
 - Focal lesions on imaging
 - Meningeal enhancement on MRI or CT

Disseminated candidiasis^d

- At least 1 of the following 2 entities after an episode of candidemia within the previous 2 weeks:
 - Small, target-like abscesses (bull's-eye lesions) in liver or spleen
 - Progressive retinal exudates on ophthalmologic examination

Mycological criteria

Direct test (cytology, direct microscopy, or culture)

- Mold in sputum, bronchoalveolar lavage fluid, bronchial brush, or sinus aspirate samples, indicated by 1 of the following:
 - Presence of fungal elements indicating a mold
 - Recovery by culture of a mold (e.g., *Aspergillus*, *Fusarium*, *Zygomycetes*, or *Scedosporium* species)

Indirect tests (detection of antigen or cell-wall constituents)^e

- Aspergillosis
 - Galactomannan antigen detected in plasma, serum, bronchoalveolar lavage fluid, or CSF
- Invasive fungal disease other than cryptococcosis and zygomycoses
 - β -D-glucan detected in serum

NOTE. Probable IFD requires the presence of a host factor, a clinical criterion, and a mycological criterion. Cases that meet the criteria for a host factor and a clinical criterion but for which mycological criteria are absent are considered possible IFD.

^a Host factors are not synonymous with risk factors and are characteristics by which individuals predisposed to invasive fungal diseases can be recognized. They are intended primarily to apply to patients given treatment for malignant disease and to recipients of allogeneic hematopoietic stem cell and solid-organ transplants. These host factors are also applicable to patients who receive corticosteroids and other T cell suppressants as well as to patients with primary immunodeficiencies.

^b Must be consistent with the mycological findings, if any, and must be temporally related to current episode.

^c Every reasonable attempt should be made to exclude an alternative etiology.

^d The presence of signs and symptoms consistent with sepsis syndrome indicates acute disseminated disease, whereas their absence denotes chronic disseminated disease.

^e These tests are primarily applicable to aspergillosis and candidiasis and are not useful in diagnosing infections due to *Cryptococcus* species or *Zygomycetes* (e.g., *Rhizopus*, *Mucor*, or *Absidia* species). Detection of nucleic acid is not included, because there are as yet no validated or standardized methods.

APPENDIX III: COG STEM CELL COMMITTEE CONSENSUS GUIDELINES FOR ESTABLISHING ORGAN STAGE AND OVERALL GRADE OF ACUTE GRAFT VERSUS HOST DISEASE (GVHD)

Reporting Requirements for Acute GVHD in COG Studies

In an attempt to standardize reporting of acute GVHD, the COG Stem Cell Transplantation Committee has adopted a modification of guidelines that were originally developed at the University of Michigan.

Table 1 outlines standard criteria for GVHD organ staging. However, confounding clinical syndromes (such as non-GVHD causes of hyperbilirubinemia) may make staging GVHD in a given organ difficult. In addition, timing of organ specific symptoms affects whether that symptom is more or less likely to be true GVHD. Please refer to **Tables 2 and 3** to assist you in deciding whether to attribute these clinical findings to GVHD, especially in situations where a biopsy is not possible. For additional help, please see the text which follows the tables.

Table 4 reviews the approach to assessing GVHD as acute, chronic, or the overlap between the two.

Finally, *engraftment syndrome* will be reported separately from the GVHD scoring presented below.

Engraftment Syndrome

A clinical syndrome of fever, rash, respiratory distress, and diarrhea has been described just prior to engraftment in patients undergoing unrelated cord blood and mismatched transplantation. If in the judgment of the local investigator a patient experiences this syndrome, details of the event should be reported when requested in the study CRFs.

Modified Glucksberg Staging Criteria for Acute Graft versus Host Disease

Table 1. Organ Staging (See tables and text below for details)

| Stage | Skin | Liver (bilirubin) | Gut (stool output/day) |
|----------|---|-------------------|---|
| 0 | No GVHD rash | < 2 mg/dL | Adult: < 500 mL/day Child: < 10 mL/kg/day |
| 1 | Maculopapular rash < 25% BSA | 2-3 mg/dL | Adult: 500-999 mL/day Child: 10-19.9 mL/kg/day Or persistent nausea, vomiting, or anorexia, with a positive upper GI biopsy. |
| 2 | Maculopapular rash 25% – 50% BSA | 3.1-6 mg/dL | Adult: 1000-1500 mL/day Child: 20-30 mL/kg/day |
| 3 | Maculopapular rash > 50% BSA | 6.1-15 mg/dL | Adult: >1500 mL/day Child: > 30 mL/kg/day |
| 4 | Generalized erythroderma plus bullous formation and desquamation > 5% BSA | >15 mg/dL | Severe abdominal pain with or without ileus, or grossly bloody stool (regardless of stool volume). |

For GI staging: The “adult” stool output values should be used for patients > 50 kg in weight. Use 3 day averages for GI staging based on stool output. If stool and urine are mixed, stool output is presumed to be 50% of total stool/urine mix.

For Stage 4 GI: the term “severe abdominal pain” will be defined as:

- (a) Pain control requiring institution of opioid use, or an increase in on-going opioid use, PLUS
- (b) Pain that significantly impacts performance status, as determined by the treating MD.

If colon or rectal biopsy is +, but stool output is < 500 mL/day (< 10 mL/kg/day), then consider as GI Stage 0.

There is no modification of liver staging for other causes of hyperbilirubinemia

Overall Clinical Grade (based on the highest stage obtained):

Grade 0: No Stage 1-4 of any organ

Grade I: Stage 1-2 skin and no liver or gut involvement

Grade II: Stage 3 skin, or Stage 1 liver involvement, or Stage 1 GI

Grade III: Stage 0-3 skin, with Stage 2-3 liver, or Stage 2-3 GI

Grade IV: Stage 4 skin, liver or GI involvement

Table 2. Evaluating Liver GVHD in the Absence of Biopsy Confirmation

Establishing liver GVHD with no skin or GI GVHD

| | | |
|---------------------------------------|--|--|
| No Skin/GI GVHD Day 0-35 | Assume no liver GVHD unless proven by biopsy | |
| No Skin/GI GVHD Day 36-100 | If NO other etiology identified, NO improvement with stopping hepatotoxic medications/TPN: Stage as liver GVHD | If other etiology identified or improves with stopping hepatotoxic drugs/TPN: Do not stage as liver GVHD |

Establishing liver GVHD with skin or GI GVHD and other cause of hyperbilirubinemia

| | | |
|------------------------------------|---|---|
| Skin and/or GI GVHD present | Worsening bilirubin level (includes worsening just prior to onset of skin or GI tract GVHD) OR stable elevated bilirubin despite resolution of non-GVHD cause of increased bilirubin: Stage as liver GVHD | Stable or improving bilirubin after diagnosis of skin or GI GVHD, irrespective of treatment: Do not stage as liver GVHD |
|------------------------------------|---|---|

Changing liver GVHD stage with other cause of hyperbilirubinemia

| | |
|--|--|
| Skin and GI GVHD stable, improving, or absent | Liver GVHD staging is carried forward without increase in stage until other disease process resolves (e.g., if TTP is diagnosed in the presence of Stage 2 liver GVHD, the liver GVHD Stage 2 is carried forward despite rising bilirubin level until TTP is resolved. If there is no liver GVHD – Stage 0 – and new onset TTP, the Stage 0 is carried forward until TTP is resolved). |
|--|--|

| | |
|---|---|
| 
Skin and/or GI GVHD worsening
 | 
Liver GVHD is staged according to the Glucksberg criteria. The elevated bili is attributed to GVHD alone.
 
Thus, when skin or GI GVHD is worsening, there is no downgrading of liver GVHD staging for other causes of hyperbilirubinemia. (e.g., if TTP is diagnosed in the presence of Stage 2 liver GVHD and worsening skin or GI GVHD, the liver is staged according to the actual bilirubin level even if some of the rise in bilirubin is attributed to TTP).
 
Similarly, even if there is no liver GVHD at onset of a new process, (such as TPN cholestasis), but skin or GI GVHD worsen during that process, then liver GVHD is diagnosed and staged according to the height of the bilirubin.
 
There is one exception to this: the diagnosis of TTP, with high LDH and unconjugated bilirubin precludes the diagnosis and staging of new liver GVHD in the absence of a confirmatory liver biopsy.
 |
|---|---|

Table 3. Evaluating GI GVHD in the Absence of Biopsy Confirmation

| 
Establishing GI GVHD with new onset diarrhea and no skin or liver GVHD
 | | |
|---|---|--|
| 
No Skin/liver GVHD Day 0 through engraftment
 | 
Assume no GI GVHD unless proven by biopsy
 | |
| 
No Skin/liver GVHD Engraftment through Day 100
 | 
NO other etiology of diarrhea identified: Stage as GI GVHD
 | 
Any other etiology of diarrhea identified: Do not stage as GI GVHD
 |
| 
Establishing GI GVHD with pre-existing diarrhea and skin or liver GVHD
 | | |
| 
Skin and/or liver GVHD present
 | 
Worsening diarrhea (includes worsening just prior to onset of skin or liver GVHD) OR persistent diarrhea despite resolution of non-GVHD cause: Stage as GI GVHD
 | 
Improving diarrhea after the diagnosis of skin or liver GVHD (irrespective of treatment) OR persistent diarrhea without resolution of underlying non-GVHD cause: Do not stage as GI GVHD
 |

Differentiating Acute GVHD, Chronic GVHD, and Overlap Syndrome

There is often confusion differentiating acute from chronic GVHD, especially in the setting of reduced intensity transplants, DLI and new prophylactic treatments. The NIH Working Group recently published new classifications for GVHD:

Table 4. Acute GVHD, Chronic GVHD, and Overlap Syndrome

| Category | Time of Symptoms after HCT or DLI | Presence of Acute GVHD features | Presence of Chronic GVHD features |
|---|-----------------------------------|---------------------------------|-----------------------------------|
| Acute GVHD | | | |
| Classic acute GVHD | ≤100 d | Yes | No |
| Persistent, recurrent, or late-onset acute GVHD | >100 d | Yes | No |
| Chronic GVHD | | | |
| Classic chronic GVHD | No time limit | No | Yes |
| Overlap syndrome | No time limit | Yes | Yes |

- Scoring of acute GVHD may need to occur past Day 100. In particular, patients should continue to be scored for acute GVHD when classic acute GVHD symptoms (maculopapular rash, nausea, vomiting, anorexia, profuse diarrhea - particularly if bloody and ileus) persist past Day 100 or if identical symptoms previously scored as acute GVHD resolve and then recur within 30 days during immunosuppression taper but past Day 100.
- Those patients being scored as having acute GVHD should NOT have diagnostic or distinctive signs of chronic GVHD.
- Patients with both acute and chronic symptoms should be diagnosed as having Overlap Syndrome and scored according to their chronic GVHD score.

Further Explanation of Criteria presented in Tables 2 and 3

Assessment of Skin GVHD

Presence or Absence of Skin GVHD: Skin GVHD will be considered present if a rash characteristic of acute GVHD develops after allogeneic marrow transplantation involving more than 25% of the body surface not clearly attributable to causes such as drug administration or infection. The extent of the body surface area involved can be estimated by the “Rule of Nines”. In estimating the extent of skin GVHD, the area involved is calculated for individual anatomic areas, such as the arm or leg, and then the total is derived from a simple summation. Areas that are non-blanching should not be considered involved regardless of the overlying color of the rash (red, brown, etc.). Limited distribution erythema (with the exception of palms and soles) in the absence of associated rash elsewhere on the body will not be considered GVHD.

Assessment of Liver GVHD

Assessing for the Presence or Absence of Liver GVHD

- A. Hyperbilirubinemia (total bilirubin ≥ 2.0 mg/dL) in the **absence** of other signs of acute GVHD in the skin or GI tract:
 - i) Day 0-35: If hyperbilirubinemia alone is present with no other signs of acute GVHD in other organ systems, acute GVHD will not be diagnosed based solely on laboratory abnormalities. Acute GVHD will be diagnosed if findings on histopathology studies of liver from a biopsy or autopsy are confirmatory.

